#### 7.3 RELEVANT CLINICAL STUDIES

# 7.3.1 Schizophrenia Studies with Oral Aripiprazole

A comprehensive clinical program to evaluate the effectiveness of oral aripiprazole monotherapy was conducted. The studies of subjects with an acute exacerbation of schizophrenia established the effectiveness of aripiprazole in the treatment of schizophrenia, including positive and negative symptoms. These studies also demonstrated its early onset of action. The long-term studies showed that aripiprazole treatment maintained stability in subjects with schizophrenia.

Two Phase 2, double-blind, placebo-controlled studies conducted in acutely relapsing hospitalized schizophrenic subjects gave support for the effectiveness, safety, and tolerability of aripiprazole in this population. Three Phase 3 studies established the efficacy of aripiprazole 10, 15, 20, and 30 mg for the treatment of acute relapse of schizophrenia or schizoaffective disorder. The two 4-week studies (31-97-201 and 31-97-202) each included two fixed doses of aripiprazole (15 mg and 30 mg for 31-97-201 and 20 mg and 30 mg for 31-97-202), an active comparator, for comparison of safety profiles, and placebo. Review of the data from these studies indicated that all of the doses of aripiprazole were effective in the treatment of acute psychosis. All aripiprazole doses were statistically significant compared with placebo with regard to the primary endpoints of change from baseline in the Positive and Negative Syndrome Scale (PANSS) total score, PANSS positive score, and Clinical Global Impression-Severity (CGI-S) score. As expected, the active comparators, haloperidol and risperidone, demonstrated effectiveness in the treatment of psychosis as measured by these endpoints. The third double-blind, placebo-controlled, Phase 3 study (CN138001) was 6 weeks in duration and included aripiprazole doses of 10, 15, and 20 mg. All doses of aripiprazole demonstrated significant improvement compared with placebo for mean change from baseline to endpoint in the PANSS total score and the positive and negative subscales.

Three Phase 3, double-blind, controlled studies were conducted to show the long-term efficacy of aripiprazole. Study CN138047 was a 26-week study designed to document the long-term efficacy of aripiprazole 15 mg compared with placebo in stable schizophrenic subjects. The primary efficacy variable was time to relapse from randomization, as measured by Clinical Global Impression–Improvement (CGI-I) score  $\geq$  5, PANSS scores for hostility or uncooperativeness  $\geq$  5, or  $\geq$  20% increase in PANSS total score. The results indicated that subjects treated with aripiprazole 15 mg daily experienced a significantly longer time to relapse over the 26-week assessment period compared with those receiving placebo. Two 52-week studies (Studies 31-98-217 and 31-98-304-01) of aripiprazole 30 mg versus haloperidol 10 mg were conducted in acutely relapsing schizophrenic subjects with the intention of pooling the data for analysis. On the primary efficacy measure (i.e., time to failure to maintain response in responders) no difference was seen between aripiprazole and haloperidol. However, analysis of secondary efficacy measures showed that aripiprazole 30 mg was superior to haloperidol for negative symptoms, depressive symptoms, and discontinuation for any reason.

The subject-rated and investigator-rated acceptability of aripiprazole treatment was examined in open-label studies. Subjects treated with open-label aripiprazole 10 to 30 mg for 8 weeks indicated a general preference for aripiprazole over the antipsychotic medication(s) taken prior to entering the study (CN138087 and CN138100). A separate open-label study (CN138152) compared aripiprazole 10 to 30 mg daily with standard of care (SOC) treatment with

Final; 26 Feb 2018 Page 16 of 80

ClinicalTrials.gov Identifier: NCT02717130

clinician-prescribed olanzapine, risperidone, or quetiapine in community-treated schizophrenic subjects for whom an alteration in antipsychotic medication was clinically warranted. Aripiprazole demonstrated superior effectiveness as measured by the Investigator's Assessment Questionnaire, which provides an overall assessment of efficacy and tolerability.

Aripiprazole showed an excellent safety and tolerability profile both in acute or chronic schizophrenia, with no evidence of increased rates of somnolence, EPS-related side effects, clinically significant weight gain, hyperprolactinemia, or prolongation of corrected QT interval (QTc). The recommended starting and target dose for aripiprazole in the treatment of schizophrenia is 10 mg or 15 mg/day administered on a once-a-day schedule without regard to meals. Aripiprazole has been systematically evaluated and shown to be effective in a dose range of 10 mg to 30 mg/day; however, there is no evidence that doses higher than 15 mg per day are associated with increased efficacy. Additional details of results of clinical studies with aripiprazole in other indications are provided in the IB.

# 7.3.2 Agitation Studies with Injectable Aripiprazole

The efficacy of immediate-release IM aripiprazole for the treatment of agitation was established in three short-term (i.e., 24-hour) placebo-controlled studies. Two studies in agitated inpatients with schizophrenia, schizoaffective disorder, or schizophreniform disorder showed that aripiprazole at doses of 5.25, 9.75, and 15 mg/day was significantly more effective than placebo for controlling agitation, as measured by change from baseline in PANSS Excited Component at 2 hours post-IM injection. A similar result was observed in agitated inpatients with bipolar disorder who received aripiprazole 9.75 mg/day.

## 7.3.3 Clinical Studies in Schizophrenia with Aripiprazole Once Monthly

Protocol CN138020, a clinical study conducted by Bristol-Myers Squibb, assessed the safety, tolerability, and PK of single doses of the aripiprazole once monthly formulation. This was an open-label, two-phase, nonrandomized, ascending dose, sequential panel study in subjects with a confirmed diagnosis of chronic schizophrenia or schizoaffective disorder. Subjects received a single 5 mg dose of the standard IM formulation followed by safety and PK monitoring. After a minimum 28-day washout, subjects who qualified based on no significant adverse events (AEs) or clinical laboratory abnormalities received a single dose of 15, 50, 100, 200, 300, or 400 mg of aripiprazole once monthly formulation, followed by safety and PK monitoring. The IM formulation appeared to be well tolerated. Peak plasma concentrations in most subjects were observed after approximately 100 hours. Most AEs were mild (43%) to moderate (33%) in severity. The most commonly reported treatment emergent AEs were headache (4 subjects, 19%) and anxiety (3 subjects, 14.3%). All other AEs occurred in ≤2 subjects. There were no discontinuations due to AEs and none of the AEs appeared to be dose-related. There were two serious adverse events (SAEs), attempted suicide and exacerbation of schizophrenia, which were considered to be unrelated to study drug.

Otsuka Pharmaceutical Development & Commercialization, Inc. (OPDC) conducted a Phase 1B study (i.e., Protocol 31-05-244) to assess the safety, tolerability, and PK of multiple doses of the aripiprazole once monthly formulation in subjects with schizophrenia. The results showed that once monthly administration of the 400-mg and 300-mg IM injections resulted in mean

Final; 26 Feb 2018 Page 17 of 80

ClinicalTrials.gov Identifier: NCT02717130

aripiprazole trough and average plasma concentrations that were comparable to the therapeutic concentrations of 10-mg to 30-mg oral aripiprazole administered daily to schizophrenic subjects. All three doses of aripiprazole once monthly (i.e., 200, 300, and 400 mg) demonstrated acceptable safety, tolerability, and potential effectiveness.

A Phase 3 study (i.e., Protocol 31-07-246) was conducted to evaluate the efficacy and safety of aripiprazole once monthly compared with placebo in schizophrenic subjects who had maintained stability on aripiprazole once monthly for at least 12 weeks. Aripiprazole once monthly 400- or 300-mg administered as monthly gluteal injections was effective for the maintenance treatment of schizophrenia in adults as demonstrated by a statistically significant difference, compared with placebo, in the primary efficacy endpoint of time to impending relapse. The percentage of subjects who met the criteria for impending relapse was significantly lower in the aripiprazole once monthly group than in the placebo group. The maintenance of stability was also demonstrated by statistically significant differences favoring aripiprazole once monthly in PANSS and CGI scores that remained significant throughout the double-blind, placebo-controlled phase. In addition, the Personal and Social Performance (PSP) Scale total score, cognitive function assessments, and Investigator's Assessment Questionnaire score were supportive of the efficacy of aripiprazole once monthly treatment. Aripiprazole once monthly was well tolerated by adult subjects with schizophrenia as demonstrated by an AE profile similar to placebo. Most treatment-emergent adverse events (TEAEs) were either mild or moderate in severity. The only TEAE reported by > 5% of subjects receiving aripiprazole once monthly and at least twice the incidence of placebo was tremor. The increased rate of tremor over placebo treatment was consistent in studies with oral aripiprazole, as also reported in the aripiprazole product labeling. Generally, AEs of tremor were mild in severity and occurred with a low frequency throughout the study. No report of tremor was classified as a SAE or was associated with discontinuation of treatment. There were no clinically relevant findings with regard to laboratory values, vital signs, weight, electrocardiogram (ECG) findings, EPS, suicidality, or injection site.

#### 7.3.4 Known and Potential Risks and Benefits

As of 10 Jun 2010, 15,088 adult subjects were treated with aripiprazole oral tablet formulation in Phase 2, 3, and 4 studies, representing 8,577 subject-exposure years. Of these, 3,901 (25.9%) subjects were treated with aripiprazole for 180 days or longer; 2,259 (15.0%) subjects received aripiprazole for at least 360 days, with 933 (6.2%) subjects continuing aripiprazole treatment for at least 720 days.

Across the short-term, double-blind, placebo-controlled studies conducted in schizophrenic subjects, the AE profile of oral aripiprazole was generally comparable to that of placebo. There was little difference in the incidence of discontinuation due to AEs between aripiprazole-treated (7%) and placebo-treated (9%) subjects. Akathisia was the only commonly observed AE that occurred in  $\geq 5\%$  of aripiprazole-treated subjects and at an incidence more than twice that of placebo (8% vs. 4%, respectively). Aripiprazole was well-tolerated in the long-term studies. Changes in body weight, fasting glucose, lipid profile, and serum prolactin levels were similar between aripiprazole- and placebo-treated subjects. No clinically relevant changes in QTc were observed in either group.

Final; 26 Feb 2018 Page 18 of 80

ClinicalTrials.gov Identifier: NCT02717130

In the pooled analysis of the two 52-week studies comparing aripiprazole with haloperidol, the incidence of EPS-related AEs was significantly higher for haloperidol (58%) compared with aripiprazole (27%). In the one 52-week study in which prolactin levels were measured, significantly fewer aripiprazole-treated subjects (3.4%) experienced prolactin elevations above the upper limit of normal (ULN) compared with the haloperidol group (61%).

The comparative safety profile of oral aripiprazole relative to placebo in subjects with acute bipolar mania raised no new safety concerns and was similar to that observed in subjects with schizophrenia. Additionally, aripiprazole exhibited a more favorable safety profile than haloperidol in the 26-week active-controlled study in acute bipolar mania. The safety profile was consistent with that observed in haloperidol-controlled schizophrenia studies, as evidenced by a lower incidence of AE discontinuation, EPS-related AEs, and prolactin elevation.

Hyperglycemia, in some cases extreme and associated with ketoacidosis or hyperosmolar coma or death, has been reported in patients treated with atypical neuroleptics. There have been few reports of hyperglycemia in subjects treated with aripiprazole. Although fewer subjects have been treated with aripiprazole, it is not known if this more limited experience is the sole reason for the paucity of such reports. Assessment of the relationship between atypical neuroleptic use and glucose abnormalities is complicated by the possibility of an increased background risk of diabetes mellitus in subjects with schizophrenia and the increasing incidence of diabetes mellitus in the general population. Given these confounders, the relationship between atypical neuroleptic use and hyperglycemia-related AEs is not completely understood. However, epidemiological studies which did not include aripiprazole suggest an increased risk of treatment-emergent hyperglycemia-related AEs in subjects treated with the atypical neuroleptics included in these studies. Because aripiprazole was not marketed at the time these studies were performed, it is not known if aripiprazole is associated with this increased risk. Precise risk estimates for hyperglycemia-related AEs in subjects treated with atypical neuroleptics are not available.

Elderly patients with dementia-related psychosis treated with atypical neuroleptic drugs, including aripiprazole, are at an increased risk of death compared with placebo. Over the course of three 10-week, placebo-controlled studies of aripiprazole in elderly subjects with psychosis associated with Alzheimer's disease, the rate of death in aripiprazole-treated subjects was 3.5%, compared with a rate of 1.7% in the placebo group during or within 30 days after termination from the double-blind phase of the studies. Although the causes of death were varied, most of the deaths were either cardiovascular (e.g., heart failure, sudden death) or infectious (e.g., pneumonia) in nature. Overall, 1.3% of aripiprazole-treated subjects reported cerebrovascular AEs (e.g., stroke, transient ischemic attack) compared with 0.6% of placebo-treated subjects in these studies. This difference was not statistically significant. However, in one of these studies, a fixed-dose study, there was a significant dose-response relationship for cerebrovascular AEs in patients treated with aripiprazole. Aripiprazole is not approved for the treatment of dementia-related psychosis. In clinical studies and postmarketing experience, accidental or intentional acute overdose of aripiprazole alone was reported in adult patients with estimated doses up to 1260 mg with no fatalities. The potentially medically important signs and symptoms observed included lethargy, increased blood pressure, somnolence, tachycardia, and vomiting. In addition, reports of accidental overdose with aripiprazole alone (up to 195 mg) in children were received with no fatalities. The potentially medically serious signs and symptoms reported included somnolence and transient loss of consciousness. In the patients who were evaluated in hospital settings, there

Final; 26 Feb 2018 Page 19 of 80

ClinicalTrials.gov Identifier: NCT02717130

were no reported observations indicating clinically important adverse changes in vital signs, laboratory assessments, or ECGs. Additional information can be obtained from the ABILIFY US package insert.

#### 7.4 STUDY RATIONALE

Non-adherence to antipsychotic medication is a well-established risk factor for symptomatic relapse. LAI antipsychotics can improve treatment adherence, but at the time of this study there were, to our knowledge, no study on the effect of LAI antipsychotics on the policy- and cost-relevant endpoint of 30-day hospital readmission rates.

The primary hypothesis was that treatment with aripiprazole once monthly would result in lower hospitalization rates for psychiatric symptom recurrence than patients experienced prior to treatment with aripiprazole once monthly.

The secondary hypotheses were that treatment with aripiprazole once monthly would result in fewer unscheduled psychiatric emergency department (ED) visits, ED visits associated with psychiatric hospitalization, and fewer total psychiatric hospitalization days than patients experienced prior to treatment with aripiprazole once monthly. In addition, we hypothesize that clinical functioning, measured by CGI-S and CGI-I scores, and change from baseline in measures of cardiometabolic risk (CMR) such as weight, body mass index (BMI), fasting glucose, and glycosylated hemoglobin (HbA1c) would improve from baseline in patients treated with aripiprazole once monthly that were previously treated with oral antipsychotics.

The study design, following well-characterized subjects for 180 days after starting aripiprazole once monthly treatment, and retrospectively reviewing data regarding prior hospitalizations, psychiatric ED visits, and prior total psychiatric hospitalization days, will allow the proposed hypotheses to be tested.

Final; 26 Feb 2018 Page 20 of 80

ClinicalTrials.gov Identifier: NCT02717130

#### 8 STUDY OBJECTIVES

#### 8.1 PRIMARY OBJECTIVE(S)

The primary objective of the study was:

• To evaluate the effect of aripiprazole once monthly on 30-, 90-, and 180-day psychiatric re-hospitalization rates following discharge due to symptoms associated with schizophrenia, compared with prior 30-, 90-, and 180-day psychiatric hospitalization rates in subjects previously treated with oral antipsychotic medication.

# 8.2 SECONDARY OBJECTIVE(S)

The secondary objectives of the study were:

#### Efficacy:

- To evaluate the effect of aripiprazole once monthly on:
  - o 30-, 90-, and 180-day rates of unscheduled psychiatric ED visits compared with prior 30-, 90-, and 180-day unscheduled visits
  - Psychiatric ED visits plus hospitalizations compared with prior 30-, 90-, and 180-day psychiatric visits plus hospitalizations
  - o Total psychiatric hospitalization days over the 180-day study period compared with the total psychiatric hospitalization days over the prior 180-day period
  - o Change from baseline in CGI-S and CGI-I scores at 30-, 90-, and 180-days
- To evaluate changes from baseline for the following indicators for CMR:
  - Weight and BMI
  - Fasting glucose concentrations
  - HbA1c concentrations
  - o Fasting plasma lipid concentrations (i.e., fasting triglyceride [primary analysis], total cholesterol, high-density lipoprotein [HDL], and low-density lipoprotein [LDL])

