# **SYNOPSIS**

Name of Sponsor: [name]. at Florida Atlantic University	
Name of Product: Abilit	fy Maintena ® , aripiprazole	
Protocol Title:	An Open-label, Multi-center, Longitudinal, Within-subject Comparison Study to Evaluate the Effects of Aripiprazole Once Monthly in Subjects with Schizophrenia on 30-, 90-, and 180-day Re-hospitalization Rates Following Hospital Discharge Compared with Retrospective Re-hospitalization Rates while on Oral Antipsychotic Medication	
Treatment Indication:	chizophrenia	
Objective(s):	The primary objective of the study was:	
	• To evaluate the effect of aripiprazole once monthly on 30-, 90-, and 180-day psychiatric re-hospitalization rates following discharge due to symptoms associated with schizophrenia, compared with prior 30-, 90-, and 180-day psychiatric hospitalization rates in subjects previously treated with oral antipsychotic medication.	
	The secondary objectives of the study were:	
	Efficacy:	
	
 
To evaluate the effect of aripiprazole once monthly on:
 
	
	
 
30-, 90-, and 180-day rates of unscheduled psychiatric emergency department
 
(ED) visits compared with prior 30-, 90-, and 180-day unscheduled visits
 
	
	
 
Psychiatric ED visits plus hospitalizations compared with prior 30-, 90-, and 180-day psychiatric visits plus hospitalizations
 
	
	
 
Total psychiatric hospitalization days over the 180-day study period compared with the total psychiatric hospitalization days over the prior 180-day period
 
	
	
 
Change from baseline in Clinical Global Impression—Severity (CGI-S) and Clinical Global Impression—Improvement (CGI-I) scores at 30-, 90-, and 180- days
 
	
	
 
To evaluate changes from baseline for the following indicators for cardiometabolic risk (CMR):
 
	
	
 
Weight and body mass index (BMI)
 
	
	
 
Fasting glucose concentrations
 
	
	
 
Glycosylated hemoglobin (HbA1c) concentrations
 
	
	
 
Fasting plasma lipid concentrations (i.e., fasting triglycerides [primary analysis], total cholesterol, high-density lipoprotein [HDL], and low-density lipoprotein [LDL])
 
	
	The exploratory objectives of the study are:	
	Safety:	
	
 
To evaluate changes from baseline to 180 days in:
 
	
	o Adverse events (AEs)	
	
 
Clinical laboratory tests (i.e., hematology, fasting clinical chemistry, prolactin, and urinalysis)
 
	

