#### **Statistical Methods:**

**Planned:** For the primary outcome, 30-, 90-, and 180-day re-hospitalization rates following aripiprazole once monthly IM injections were to be compared with prior 30-, 90-, and 180-day hospitalization rates in subjects previously treated with oral antipsychotic medication. Descriptive statistics were to be provided for all efficacy variables and safety variables. Continuous variables, including fasting laboratory values, were to be summarized by tabulations of mean, median, range, and standard deviation using change from baseline to 30-, 90-, and 180-day values. Tabulations of frequency distributions were provided for categorical variables. The primary and secondary outcomes were to be analyzed using repeated measures analysis of covariance models.

Actual: No statistical analyses were performed

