HealthNet (Medicaid) and Missouri Department of Mental Health (DMH) data via collaboration with the Missouri Institute of Mental Health (MIMH) or confirmed through all available medical records and reliable data from caregivers. Availability of Medicaid data or documentation of at least one inpatient hospitalization, ED visit, or equivalent (i.e., urgent care center) visit within the previous 6 months of screening was required for eligibility (see inclusion and exclusion criteria, Section 9.3).

- Admission vital signs (e.g., blood pressure, heart rate, respiratory rate, and temperature)
- Admission height, weight, and calculation of BMI
- Admission ECG
- Admission HbA1c, if available
- Admission safety clinical laboratory tests (Section 9.5.1.4.1)
- Admission clinical laboratory results were assessed to rule out exclusionary values (Section 9.3)
- Urine pregnancy test for women of childbearing age
- Previous medications taken within 30 days prior to starting study drug were recorded.
   Concomitant medications including details (e.g., drug name, dose, and frequency) of all current medication(s) and any antipsychotic medications taken within 6 months of screening were recorded.
- The nature of acute hospitalization in this population could indicate prior discontinuation of antipsychotic medications due to noncompliance. Appropriate review of all medications for psychiatric illness, including newly prescribed antipsychotic medication was conducted during screening. Discontinuation or tapering of any psychotropic medication, if deemed clinically appropriate or necessary for those subjects entering Phase A (i.e., Oral Tolerability Phase), started at screening and continued during Phase A.
- Additional clinical laboratory tests (fasting or non-fasting as needed) which were not obtained at admission, were deemed necessary by the PI and/or were required to verify inclusion and exclusion criteria

Fasting or non-fasting clinical laboratory tests that were required to establish eligibility could be performed at any time during the Screening Period. Study specific clinical laboratory tests that required fasting (i.e., fasting lipid profile and fasting glucose) were performed during the Baseline Visit.

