## Efficacy:

- Comparison of:
  - o 30-, 90-, and 180-day rates of unscheduled psychiatric ED visits compared with prior 30-, 90-, and 180-day unscheduled visits
  - Psychiatric ED visits plus hospitalizations compared with prior 30-, 90-, and 180-day psychiatric visits plus hospitalizations
  - Total psychiatric hospitalization days over the 30-, 90- and 180-day study period compared with the total psychiatric hospitalization days over the prior 30-, 90- and 180-day period
  - o Change from baseline in CGI-I, based on the initial CGI-S, and CGI-I scores at 30-, 90-, and 180-days
- Changes from baseline on the following indicators for CMR after receiving aripiprazole once monthly:
  - Weight and BMI
  - o Fasting glucose concentrations, HbA1c concentrations, and fasting lipids concentrations (i.e., fasting triglyceride, total cholesterol, HDL, and LDL)

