## 9.7.1.9 Efficacy Analyses

The primary objective of the study was to evaluate the effect of aripiprazole once monthly on 30-, 90-, and 180-day psychiatric re-hospitalization rates following discharge due to symptoms associated with schizophrenia, compared with retrospective 30-, 90-, and 180-day psychiatric hospitalization rates in subjects previously treated with oral antipsychotic medication.

Because all primary and secondary outcome measures described in the specific aims were continuous and a reflection of a single design configuration involving longitudinal measures, in some cases including retrospective as well as prospective time points, the basic structure of the data analytic strategies was the same for all objectives.

The primary and secondary outcomes were to be analyzed using repeated measures analysis of covariance (ANCOVA) models. For example, in the three primary outcome models, testing for a main effect of time on 30-, 90-, or 180-day pre-hospitalization (i.e., oral antipsychotic) versus 30-, 90-, or 180-day post-hospitalization (i.e., aripiprazole once monthly) rates, respectively. Covariates would have included psychiatric symptoms severity at baseline, measured by CGI-S scores.

Some secondary outcome measures such as BMI, fasting lipid parameters, and glucose that were measured at time points post-hospitalization only (i.e., at baseline, 30-, 90-, and 180-days) were to be evaluated using mixed model repeated measures analysis of variance to determine whether there are changes over time. Other covariates could include race, gender, age, family history of diabetes, and BMI.

Only one primary specific objective was defined, with three time-point comparisons (i.e., 30, 90, and 180 days) with the primary comparison being hospitalization rate for the period of 30 days pre-hospitalization (i.e., at least one, based on the index hospitalization) to 30 days post-hospitalization both because of the importance of that objective and to minimize multiple comparisons concerns. Because of the multiple comparisons issue, p-values associated with the secondary and exploratory analyses performed were to be interpreted cautiously as hypothesis-generating rather than as hypothesis-confirming.

Final; 26 Feb 2018 Page 56 of 80

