## 9.7.1.10 Other Analyses

In general, continuous variables were to be summarized by descriptive statistics (i.e., n, mean, median, SD, standard error, maximum, and minimum). The repeated measures ANCOVA was used based on the Phase B sample. The variables relating to hospitalization data were to be comparing retrospective versus prospective data. The number of hospital stays per subject, cumulative duration of hospitalization, mean duration of hospitalization, and the number and mean duration of all other (i.e., non-inpatient) hospitalization programs were to be compared between the SOC and aripiprazole once monthly by ANCOVA and summarized using descriptive statistics. The Kaplan-Meier estimate of the median discontinuous time and the overall Kaplan-Meier curve for the Phase B efficacy sample were to be provided for the time-to-discontinuation due to all causes. In addition, discontinuation rate due to all reasons, change from baseline in CGI-S and CGI-I scores were to be summarized using descriptive statistics for the Phase B efficacy sample.

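### CGI-S change and fasting-glucose change at Days 30, 90 and 180 are planned, but Table 3 schedules CGI-S at Screening only and has no fasting-glucose row

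*Combined protocol and SAP*

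**What the plan says.** **CGI-S.** The secondary objective in Section 8.2 (and the Synopsis) is "Change from baseline in CGI-S and CGI-I scores at 30-, 90-, and 180-days". Section 9.7.1.10 adds that "change from baseline in CGI-S and CGI-I scores were to be summarized using descriptive statistics for the Phase B efficacy sample". The rationale in Section 7.4 states "we hypothesize that clinical functioning, measured by CGI-S and CGI-I scores, and change from baseline in measures of cardiometabolic risk", among other measures, and expects improvement. The endpoint list in Section 9.7.1.2 is worded differently: "Change from baseline in CGI-I, based on the initial CGI-S, and CGI-I scores at 30-, 90-, and 180-days". Table 3 marks CGI-S in the Screening column and nowhere else. The assessment lists for Baseline (9.1.4.1) and the Treatment Phase (9.1.4.2) name CGI-I but not CGI-S.

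**Fasting glucose.** It is a cardiometabolic objective in Section 8.2 and an endpoint in Section 9.7.1.2. Section 9.7.1.9 describes a repeated-measures model for BMI, lipids and "glucose that were measured at time points post-hospitalization only (i.e., at baseline, 30-, 90-, and 180-days". The Synopsis says "Continuous variables, including fasting laboratory values, were to be summarized by tabulations of mean, median, range, and standard deviation using change from baseline" to Days 30, 90 and 180. On collection, Section 9.1.2 says "Study specific clinical laboratory tests that required fasting (i.e., fasting lipid profile and fasting glucose) were performed during the Baseline Visit". Section 9.5.1.4.1 refers sampling times to Table 3. That table has rows for fasting lipids, HbA1c and prolactin, and none for fasting glucose.

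**The concern.** A change score needs a second rating, and for CGI-S none is scheduled. Sites following the plan exactly would deliver no data for that part of a secondary objective and hypothesis. The missing-data rule cannot help, because the LOCF data set in Section 9.7.4.1 does not carry baseline forward, so there would be nothing to impute from.

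The glucose problem is different in kind. Values could exist, but only where someone chose to order chemistry. If sites treat fasting glucose as part of the discretionary safety panel, the Day 30, 90 and 180 values come from subjects tested for clinical reasons. The bias that follows has unknown direction and size. Table 2 lists fasting glucose separately from chemistry glucose, so even that reading is not certain.

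The documents also disagree with each other. The objective implies repeated CGI-S ratings, while the endpoint list fits a single initial one.

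**Working it through.** The main check sets each planned analysis time point against Table 3. No sample-size or power figure is involved.

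**Scheduled assessments (Table 3)**

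| Measure | Screening | Baseline | Day 30 | Day 90 | Day 180 | Required post-baseline |
|---|---|---|---|---|---|---|
| CGI-S | yes | no | no | no | no | 0 of 3 |
| CGI-I | no | yes | yes | yes | yes | 3 of 3 |
| Fasting lipids | yes | yes | yes | yes | yes | 3 of 3 |
| HbA1c | yes | yes | yes | yes | yes | 3 of 3 |
| Fasting glucose | no row | no row | no row | no row | no row | 0 of 3 |

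**Could glucose enter by another row?** Footnote n limits the lipid row to total, HDL and LDL cholesterol and triglycerides. Footnote l places glucose in the safety chemistry, done at Screening and later only when clinically necessary. Footnote r leaves every entry in that row from Baseline to Day 180 to the Principal Investigator's judgement of safety need. Section 9.1.4.2 treats additional laboratory testing in the same way. The statement in Section 9.1.2 covers the Baseline Visit only, and neither the Table 3 grid nor the Section 9.1.4.1 list carries it.

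**Reported data, as illustration**

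- *CGI-S.* Table 5 gives 1 moderately, 5 markedly and 2 severely ill: (1×4 + 5×5 + 2×6)/8 = 41/8 = 5.125. The squared deviations sum to 2.875, so SD = √(2.875/7) = 0.64. This matches the Screening entry 5.13 (0.64) in Table 8. All 10 later columns are N/A.
- *Fasting glucose.* Table 7 prints panel counts of 2 at Day 30, 3 at Day 120 and 1 at Day 180. Fasting glucose is 90.00 (9.90), 86.00 (16.46) and not done. There is no Day 90 column. At the three analysis days that is 2 + 0 + 0 = 2 reported values.
- *Counts for Table 8.* Only Day 180 has a printed n (1). The others were inferred from rounded means and SDs.
  - CGI-I, n from 2 to 8: the Day 30 mean of 2.80 is possible only as 14/5, so n = 5. The Day 90 mean of 2.75 needs n = 4 or 8. With n = 8 the sum is 22 and the sum of squares must be even. The nearest values give SD √(5.5/7) = 0.89 or √(7.5/7) = 1.04, not 0.96, so n = 4.
  - Lipids, assumed whole mg/dL, n from 2 to 5: Day 30 triglycerides of 68.50 (24.09) need an even n. With n = 2 the sum is 137 and the two values differ by an odd number, giving SD 33/√2 = 23.33 or 35/√2 = 24.75. Neither fits, so n = 4. Day 90 means ending in .75 (186.75, 84.75, 58.75) need n = 4.
- *Totals at Days 30, 90 and 180.* CGI-I 5 + 4 + 1 = 10; fasting lipids 4 + 4 + 1 = 9; fasting glucose 2; CGI-S 0. At most 2 of the 9 lipid results have a fasting glucose in Tables 7 and 8, so at least 7 of 9 do not.

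**The case against.** **CGI-S is leftover wording.** Table 3, both visit lists and the endpoint list all fit one CGI-S rating, and only the objective, the rationale and Section 9.7.1.10 imply more. That is fair, and it makes deletion a legitimate repair. It does not remove the contradiction.

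**Glucose is in Table 3.** Footnote l names it, footnote k asks for at least 10 hours' fasting before all laboratory draws, and the safety row is marked at every visit from Baseline to Day 180. This stands as a qualification: what is missing is a required draw. Footnote k governs how a sample is taken, not whether one is taken. It is also true that Section 8.2 gives no days for glucose and Section 9.7.1.9 does not say fasting. The days come from that section and the Synopsis.

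**The reported data do not track the schedule.** Lipids are scheduled at Baseline yet shown as N/A on Day 1. Lipids and HbA1c appear at Day 120, and prolactin at Days 60, 90 and 120, where no row calls for them. Fasting glucose was reported at Day 120, though that is not a planned analysis day. Appendix 2, said to hold the efficacy data collected, shows only a heading in the available text. The missing glucose values therefore cannot be attributed to the missing row. This stands: the reported counts illustrate the gap, and the evidence for it is the schedule.

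**Limited consequence.** Both outcomes are secondary, Section 9.7.1.9 treats their p-values as hypothesis-generating, and the study stopped early without formal analysis. This is correct and limits the weight of the point.

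**Conclusion.** The concern holds. As written, the plan schedules 0 of 3 post-baseline CGI-S ratings and requires 0 of 3 post-baseline fasting-glucose draws, while planning change analyses that need both. The CGI-S change cannot be computed, and the glucose model would rest on discretionary samples. The schedule counts are read directly from Table 3 and need no assumption. The reported counts rest on small numbers, on sizes inferred from rounded summaries with whole-number lipids assumed, and on Tables 7 and 8 alone. They give no rate for a full trial. The primary endpoint data are not affected. This should be corrected, but it does not threaten the main comparison.

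**What to change.** 1. **CGI-S.** Choose one of two repairs.
   - Add CGI-S to Table 3 and to Sections 9.1.4.1 and 9.1.4.2 at Phase B Baseline and Days 30, 90 and 180, where CGI-I is already scheduled. This is needed if the Section 7.4 hypothesis is kept. It costs a few minutes of rater time at four visits.
   - Delete CGI-S change from the Synopsis, Section 8.2 and Section 9.7.1.10, and CGI-S from the Section 7.4 hypothesis. This costs only text, agrees with Section 9.7.1.2, and gives up that part of the hypothesis.
2. **Covariate.** In Section 9.7.1.9, state before analysis which CGI-S rating is the severity covariate. Naming the Screening rating uses data already scheduled, and under deletion it is the only rating available. A new Baseline rating would change the covariate in the primary model. For subjects enrolled after the first injection it would be taken after treatment began.
3. **Fasting glucose.** Add a row to Table 3 at Baseline and Days 30, 90 and 180, beside the fasting lipids and exempt from footnotes l and r. Name it in Sections 9.1.4.1 and 9.1.4.2. The cost is one local analyte at four visits already scheduled. Use of the same blood sample is an assumption.
4. **Minor wording.** CGI-I already rates change, so analyse the post-baseline score itself without subtracting the Day 1 rating. Reconcile the Section 9.7.1.2 wording with the Phase B baseline anchor in Section 9.5.1.8.1. Table 2 footnote a and Section 9.5.1.3 limit triglycerides to Screening, so align both with Table 3, which schedules them later as well.
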